4.4.2 Other Missing Data

Any other partial date of relevance (for example, date of last study contact at the time of database lock will be imputed as follows:

- If the day is missing, 15th of the month, or the randomization date (if participant randomized after 15th of the same month and same year) will be used, making sure the imputed date is not post end of study date.
- If the month is missing, June, or the randomization month (if participant randomized after June and year of the event is same as randomization year) will be used, making sure the imputed date is not post date last known alive on end of study form.

4.5 Assessment of Model Assumption

The validity of the proportional hazards assumption made in the secondary analysis will be examined using standard graphical methods such as Log (-log) plots; if the assumption holds the curves should be approximately parallel to each other.

An additional analytical method that includes treatment*log (time) as a factor in the model and tests the interaction factor at the 0.05 significance level may be employed; non-significance ($p>0.05$) of this factor would suggest proportionality.

If there is evidence of non-proportionality its cause will be investigated by exploring hazard ratios within few pre-specified clinically meaningful time landmarks such as every six months.

5 OUTCOMES

Please refer to Section 10.2 of the CSP for information on which endpoints are adjudicated.

5.1 Primary Outcome

The primary outcome follows an ordinal scale of clinical severity comprised of 1) confirmed death at one year, 2) number of confirmed hospitalizations for heart failure evaluated at one year; or 3) change in 6MWT from baseline evaluated at 6 months.

We will rank all participants from the lowest to the highest based on their 12-month experience, regardless of their treatment assignment.

Each participant from the treatment arm gets ranked/compared with each participant from the control arm based on the 12-month experience for Death and Hospitalizations for heart failure and 6 month results for change in 6MWT to determine treatment response per the following hierarchy:

1. Death

If both die, the one who survives longer is better off;
If one dies and one does not, the one that survives is better off;
If neither dies, examine hospitalizations for heart failure.

2. Hospitalizations for heart failure

The one with fewer hospitalizations is better off
If neither has been hospitalized for heart failure or the number heart failure hospitalizations is equal, compare change in 6MWT.

3. Change in 6MWT

The one with higher change in 6MWT is better off;

Any ties that cannot be resolved by change in 6MWT remain as ties.

5.2 Top Secondary Outcome

The top secondary outcome is defined as the time from randomization to the onset of first confirmed event in the composite CV outcome of CV-related death (any deaths confirmed as unknown are included in CV deaths) or hospitalization for heart failure.

In the unlikely event that two confirmed outcomes occur on the same day, the following hierarchy will be used to ascribe the primary component of the composite:

- CV-related death
- Hospitalization for heart failure

5.3 Analyses of the Primary and the Top Secondary Outcome

The analytic approaches for the primary and top secondary outcome are detailed in below sections.

5.3.1 Nonparametric Test of FCM vs. Placebo for Primary Composite

The null hypothesis being tested is that a randomly chosen participant in the treatment arm is equally likely to be ranked better or worse than a randomly chosen participant in the control group. The two-sided alternative is that the participant is not equally likely to be ranked better or worse.

In addition to performing the test, we will estimate the probability that a participant in the treatment arm has a better rank than a participant in the control arm and its corresponding confidence interval.

The main comparison will be conducted using the Wilcoxon-Mann-Whitney test in ITT population relying on multiple imputation model as summarized in Section [4.4.1](#).

The above comparison of participants in the treatment versus control arms is equivalent to ranking all participants according to their experience. At one end of the ranking are participants with the best experience - those alive and not hospitalized for worsening heart failure ordered according to their improvement in 6MWT; at the opposite end are those who die ordered according to their survival time. Those participants alive but hospitalized are in the middle, ordered according to their number of hospitalizations for worsening heart failure and then by their change in 6MWT. The non-parametric Wilcoxon-Mann-Whitney test sums the ranks of those in the treatment arm and compares them with the sum of ranks in the control arm.

Win-Ratio and its confidence intervals will be calculated to aid in interpretation of the results for primary efficacy analysis. The unmatched pair win ratio will be calculated by adding all wins from treatment group and dividing it by all wins from placebo group. The confidence interval will be calculated using the supplementary material for the reference ([Pocock 2012](#)).

In all analyses, the number of hospitalizations (and the number of days in the hospital in the sensitivity analysis described in Section 5.3.1.1) will be adjusted for the time in follow-up. This will be accomplished by dividing the observed number by time at risk in years. For individuals who complete the pre-specified 12 months of follow-up, time at risk equals 1. For all others, it is equal to the fraction of 12 months that the person remained in the study.

5.3.1.1 Sensitivity Analysis (Additional Layer to Hierarchy) for Nonparametric Test of FCM vs. Placebo for Primary Composite

In a sensitivity analysis we will add another layer to the hierarchy described above – in individuals who have been hospitalized for heart failure during follow-up, ties in the numbers of hospitalizations will be resolved based on the total number of days in the hospital during follow-up, before proceeding to comparison of differences in the 6MWT using the primary analytic method. This will be conducted in the ITT population only.

5.3.1.2 Sensitivity Analysis for Potential Covid-19 Impact for Nonparametric Test of FCM vs. Placebo for Primary Composite

In case there are 5% or more of randomized participants with missing 6 month 6MWT due to COVID-19 (those with visits not performed or visit type modified due to Covid-19) who also did not have a qualifying clinical event (death or heart failure hospitalization through 1 year), then we will assess the sensitivity of primary results to the missing 6MWT data by conducting a tipping point analyses on the primary analyses method in ITT population.

The tipping point analysis will assume progressively biased tie breaking for 6MWT distance missing due to COVID-19 varying from worst distance favouring the placebo to the best distance. Hence, starting with all missing 6MWT values favouring the placebo to break the tie and checking if this does not change inference from the primary analyses. However, if it does change the inference then we will continue going down the scale to find the tipping point. The 6MWT distance at 6 months missing for non-COVID-19 reasons will be imputed as for primary analysis.

5.3.1.3 Sensitivity Analysis for Russia Ukraine War Impact (censor the data after invasion) for Nonparametric Test of FCM vs. Placebo for Primary Composite

We plan to conduct two different sensitivity analyses to assess the impact of the Russia-Ukraine war. In the first of these two analyses we will censor the data from Russia and Ukraine for the hierarchical primary composite endpoint with a date after invasion (24 February, 2022), before proceeding to comparison of the endpoint using the primary analytic method. This will be conducted in the ITT population only.

5.3.1.4 Sensitivity Analysis for Russia Ukraine War Impact (exclude participants from these two countries) for Nonparametric Test of FCM vs. Placebo for Primary Composite

As a second sensitivity method to assess the impact of the war on the hierarchical primary composite, we will exclude participants from Russia and Ukraine for comparison of the endpoint using the primary analytic method. This will be conducted in the ITT population only.

5.3.1.5 Sensitivity Analysis to account for Clinically Meaningful Difference in Change from Baseline in 6MWT for Nonparametric Test of FCM vs. Placebo for Primary Composite

In this sensitivity analysis of hierarchical primary composite, we will use the win-ratio method with the additional condition of requiring a change from baseline in 6MWT for the participant to be 10 and 20 meters respectively to be considered clinically meaningful ([Khan 2022](#)). Hence, if two participants are tied based on their data on death time and number of HF hospitalizations within 1 year, further tie-breaking will require 10 meters and 20 meters difference in 6MWD change when they are compared for win-ratio analysis. Only the win-ratio and its 95% confidence interval will be computed. This analysis will be conducted in the ITT population only.

5.3.1.6 Key Supportive Analysis for Nonparametric Test of FCM vs. Placebo for Primary Composite

As the key supportive analysis, the null hypothesis for the primary composite end point, that a randomly chosen participant in the treatment arm is equally likely to be ranked better or worse than a randomly chosen participant in the control group, will be tested using the same approach as in the primary analysis based on PP population.

In case of a difference in inference between the primary analysis and the key supportive analyses, further exploratory analyses will be conducted to understand the reason for a possible difference.

5.3.1.7 Supportive Analysis (Impute to Worst Possible 6MWT Distance at 6 Months) for Nonparametric Test of FCM vs. Placebo for Primary Composite

As supportive analysis, we will impute the worst possible 6MWT distance at 6 months as the component for primary hierarchical composite for all individuals who do not have this measurement, regardless of the reason. We will use the primary analytic method here and the analysis will be conducted in the ITT population only.

5.3.1.8 Supportive Analysis (Tipping Point) for Nonparametric Test of FCM vs. Placebo for Primary Composite

We will perform tipping point assessments to determine the sensitivity of the primary efficacy result to the missing 6 month 6MWT distance data. The tipping point analysis will assume progressively biased tie breaking. Hence, starting with all missing 6MWT values favouring the placebo to break the tie and checking if this does not change inference from the primary analyses. However, if it does change the inference then we will continue going down the scale to find the tipping point. This will be conducted in the ITT population only.

5.3.1.9 Supportive Analysis (Total burden of HF impact) for Nonparametric Test of FCM vs. Placebo for Primary Composite

To further understand the burden of the disease, we will analyse a combined endpoint of CV death and frequency of intervention for worsening heart failure (hospitalization or urgent heart failure visits), through the duration of the study. The analytic methods will follow that for the primary analyses. The analysis will be conducted in the ITT population only.

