8.6 Primary Comparison

Each participant from the treatment arm gets ranked/compared with each participant from the control arm based on the 12-month experience for Death and Hospitalizations for heart failure and 6 month results for change in 6MWT to determine treatment response per the following hierarchy:

1. Death

- If both die, the one who survives longer is better off;
- If one dies and one does not, the one that survives is better off;
- If neither dies, examine hospitalizations for heart failure.

2. Hospitalizations for heart failure

- The one with fewer hospitalizations is better off;
- If neither has been hospitalized for heart failure or the number heart failure hospitalizations is equal, compare change in 6MWT.

3. Change in 6MWT

- The one with higher change in 6MWT is better off;

Statistical Test

The main comparison will be conducted using the Wilcoxon-Mann-Whitney test. The null hypothesis being tested is that a randomly chosen participant in the treatment arm is equally likely to be ranked better or worse than a randomly chosen participant in the control group. The two-sided alternative is that the participant is not equally likely to be ranked better or worse. In addition to performing the test we will estimate the probability that a participant in the treatment arm has a better rank than a participant in the control arm and its corresponding confidence interval.

The above comparison of participants in the treatment versus control arms is equivalent to ranking all participants according to their experience. At one end of the ranking are participants with the best experience - those alive and not hospitalized for worsening heart failure ordered according to their improvement in 6MWT; at the opposite end are those who die ordered according to their survival time. Those participants alive but hospitalized are in the middle, ordered according to their number of hospitalizations for worsening heart failure and then by their change in 6MWT. The non-parametric Wilcoxon-Mann-Whitney test sums the ranks of those in the treatment arm and compares them with the sum of ranks in the control arm.

In all analyses the number of hospitalizations (and the number of days in the hospital in the sensitivity analysis described below) will be adjusted for the time on follow-up. This

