1.3 Randomization and Blinding

The randomization scheme was generated by a statistician at DCRI who is firewalled to the operational team, using Statistical Analysis System (SAS v9.4) with region as the only stratification field. Blocking was used in the scheme with random block sizes (3 different levels). This scheme was implemented into the Interactive Web Response Systems (IXRS) by the vendor Almac. The vendor maintains randomized treatment assignments as well as unblinded kit dispensation information. The operational team for this trial is to remain blinded until data base lock, at which time the unblinded treatment codes received from Almac will be combined with blinded data.

In the event of the need to break an individual participant blind, the site can call Almac for this information. The operational team gets informed if such unblinding occurs; however, they do not know the true treatment assignment.

The 3 regions are defined within the randomization scheme as follows (Details can be found in the SAP Appendix for Definitions and Reporting Conventions):

- North America
- Asia Pacific
- Europe

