Unless otherwise stated, timings of efficacy endpoints will be relative to the date of randomization. Specifically, for all time-to event analyses (defined as [event date – randomization date] +1 where event occurs and as [appropriate censoring date based on analytic population – randomization date] +1 where event does not occur), the treatment groups will be analysed using a Cox proportional hazards model that includes treatment as an explanatory factor, region as stratification factors along with pre-specified baseline covariates: age, sex, ejection fraction, NYHA class, heart failure etiology (Ischemic vs. non-ischemic (unknown etiology considered as non-ischemic)), NT-proBNP, haemoglobin, ferritin, TSAT, eGFR and BMI, unless specified otherwise. If any of the pre-specified baseline covariates have >5 participants with missing data, they will not be used in the analyses to maintain the ITT population for the model. If the baseline covariate is missing data on ≤ 5 participants, we will impute the missing value with overall mode if categorical covariate and the overall mean if continuous variable. The Efron method will be used for handling ties. P-value and confidence intervals for the HR will be based on the Wald statistic. Any analyses using events that are confirmed by the CEC will use the CEC adjudicated responses and related dates. Analyses of Cardiovascular (CV) death, will include deaths with cause of death confirmed as unknown. In addition, the summary tables of these analyses will include the number of participants with event and the cumulative incidence (1 – the “survival” or event-free proportion) over time per treatment group presented annually through the last time point where 90% of the overall events have occurred. Cumulative incidence function and Kaplan-Meier estimates of participants with events will also be calculated and plotted through maximum follow up available in the study, with number of participants at risk indicated below the plot at specific times.

We will present empirical cumulative distribution function curves by treatment of change in 6MWT distance at 6 and 12 months.

For all the hierarchical composite endpoints, in addition to primary analytic method, we will present win-ratio along with its confidence interval.

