4.4 Handling of Missing Data

4.4.1 Outcome Data/Dates

The primary analysis will rely on a multiple imputation model, with Markov chain Monte Carlo algorithm based on the totality of observed data. One exception to this rule will be that

individuals unable to perform the 6MWT test at 6 months i.e. those who did not perform a 6MWT or died prior to 180 days will have their value imputed as the worst possible 6MWT distance which is 0 meters. Any missing death dates will be imputed using date imputation rules in this section. A baseline 6MWT distance is needed to be able to calculate change from baseline 6MWT, hence, any missing baseline 6MWT distance will be imputed as overall mean to allow full ITT population to be included in primary analyses.

The SAS PROC MI procedure will be used for multiple imputations on the 6 month 6MWT distance, with 20 imputations. To ensure consistency in the imputed data for future possible validations, a seed number will be fixed to 1000. Baseline 6MWT, treatment and region will be included as covariates in the imputation model. We will include all observed data in the imputation model with the exception of participants unable to perform 6MWT at 6 months who will have their 6MWT distance included as 0 meters before performing multiple imputation. Imputed data set(s) will include an index variable to identify the number of imputed data. The results across the imputed datasets will be combined using Rubin's rule ([Rubin 1987](#)) to obtain one set of results for the primary analysis. These same missing data handling rules will be used for the Win-Ratio analyses. Basic statistics on the overall original data (incomplete data) and the data following imputation will be provided in the Clinical Study Report (CSR).

For secondary efficacy endpoints, missing data relating to the indicator for the confirmed composite CV outcome and/or its components will not be imputed. Any partial or completely missing date for a confirmed composite CV outcome at the time of database lock will be imputed as follows:

- If the day is missing, 15th of the month, or the randomization date (if participant randomized after 15th of the same month and same year) will be used, making sure the imputed date is not post date last known alive on end of study form;

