5.3.2 FCM vs. Placebo for Top Secondary Outcome

This analysis will compare time from randomization to the first occurrence of CV death or hospitalization for heart failure. The Cox proportional hazards model will be employed to conduct this comparison. The Cox model will include treatment, region as a stratification variable and will be adjusted for pre-decided baseline covariates as noted in section 4.1. The test will be two-tailed and will be performed at an overall α of 0.04. This analysis will be performed by the ITT principle based on randomized treatment assignment and we expect adequate power to detect a pre-specified relative risk reduction of 20%.

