5.5 Secondary Outcomes

All other secondary outcomes are listed and defined below. These secondary outcomes will be tested in the order listed below and are considered as supportive in the assessment of the effect size attributable to FCM and will be analysed in ITT only and without a multiplicity adjustment.

- (1) Mean change in 6MWT distance from baseline to 12 months will be compared using linear regression adjusting for baseline value of 6MWT distance and region. We will not adjust for other baseline covariates.
- (2) Time to CV deaths or intervention for worsening heart failure (hospitalization or urgent heart failure visits) defined as time from randomization to the earliest of confirmed CV death or confirmed intervention for worsening heart failure will be compared using the Cox proportional hazards model.
- (3) Time to CV deaths or CV hospitalizations defined as time from randomization to the earliest of confirmed CV death or confirmed CV hospitalization will be compared using the Cox proportional hazards model.
- (4) Time to CV deaths defined as time from randomization to confirmed CV death (deaths confirmed as “Unknown” type will be included in the CV death counts) will be compared using the Cox proportional hazards model.

- (5) Time to non-cardiovascular deaths defined as time from randomization to confirmed non-CV death will be compared using the Cox proportional hazards model.
- (6) Time to first confirmed hospitalization for myocardial infarction (MI) defined as time from randomization to the earliest confirmed hospitalization for MI will be compared using the Cox proportional hazards model.
- (7) Time to first confirmed hospitalization for stroke defined as time from randomization to the earliest confirmed hospitalization for stroke will be compared using the Cox proportional hazards model.
- (8) Time to first confirmed hospitalization for other CV event defined as time from randomization to the earliest confirmed hospitalization for other CV event will be compared using the Cox proportional hazards model.
- (9) Time to first confirmed urgent heart failure visit defined as time from randomization to the earliest confirmed urgent heart failure visit will be compared using the Cox proportional hazards model.

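### The primary Wilcoxon test and win ratio leave out region, the only randomization stratum; if regions differ, the test is slightly conservative and gives up a little power.

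*Combined protocol and SAP*

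**What the plan says.** SAP v1.3 section 1.3 describes blocked randomization "with region as the only stratification field", with three regions: North America, Asia Pacific and Europe. Section 1.2 gives the 1:1 ratio.

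For the primary endpoint, section 5.3.1 states: "The main comparison will be conducted using the Wilcoxon-Mann-Whitney test in ITT population relying on multiple imputation model". Protocol v3 section 8.6 names the same test: "The main comparison will be conducted using the Wilcoxon-Mann-Whitney test". All participants are ranked together. The win ratio is also pooled: "The unmatched pair win ratio will be calculated by adding all wins from treatment group", divided by all placebo wins. None of the sensitivity and supportive analyses in 5.3.1.1 to 5.3.1.9 stratifies the rank test by region. Region enters the primary analysis only through the missing-data step in section 4.4.1: "Baseline 6MWT, treatment and region will be included as covariates in the imputation model".

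Other efficacy models use region directly:
- SAP 4.1, all time-to-event analyses: "region as stratification factors along with pre-specified baseline covariates".
- SAP 5.3.2, top secondary outcome: "The Cox model will include treatment, region as a stratification variable".
- SAP 5.5, 12-month walk change: "linear regression adjusting for baseline value of 6MWT distance and region". In SAP v1.0 the same regression adjusted for baseline distance only, so region was added later.

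The final two-sided level for the primary test is 0.0099 (SAP 1.4). The primary and top secondary outcomes are tested in sequence (SAP 4.2).

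**The concern.** Blocking within region makes the arms nearly equal in size in each region, so differences between regions cannot contribute to the treatment contrast. The pooled Wilcoxon variance still includes the spread of ranks between regions. It is therefore larger than the true sampling variance whenever region predicts rank, and the z statistic is too small.

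Putting region in the imputation model does not cure this. It affects the values filled in for missing walks, not the test statistic or its variance.

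At stake is efficiency in the test that opens the sequence, at a strict alpha, together with consistency between the analysis and the randomization. The validity of a positive result is not in question.

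**Working it through.** **Inputs from the documents.** N = 3014 (1507 per arm), alpha 0.0099, 15% missing 6MWT, and the SAP Table 1.4.1 tiers:
- death 8% vs 6.8%;
- one, two, and three or more hospitalizations in survivors 6/3/1% vs 4.8/2.4/0.8%;
- walk change mean 0 vs 18 m, SD 90.

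**Inputs assumed.** Regional shares, event-rate multipliers and walk shifts, because the documents give none. The treatment effect is taken as the same in every region.

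**Step 1, the plan's own figure.** The plan states 90% power. Simulating the pooled test gives 91.8% with the 15% missing walks ranked worst in their tier and 2.5% lost to follow-up ranked lowest. Other ways of ranking missing walks worst give 92.7% to 95%. Neutral handling gives 98% to 99%. The plan does not say how its simulation treated missing walks, and this point does not depend on that.

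**Step 2, analytic size and power.** Let η² be the share of rank variance lying between regions, and c = Φ⁻¹(1 − 0.0099/2) = 2.579. Under region-balanced allocation the pooled z has null variance 1 − η², so:
- actual size = 2[1 − Φ(c/√(1 − η²))];
- pooled power = Φ(θ − c/√(1 − η²)), where θ = c + 1.282 = 3.861 gives a stratified test 90% power.

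Example with η² = 0.0659: √(1 − η²) = 0.9665, and 2.579/0.9665 = 2.669. Size is 2[1 − Φ(2.669)] = 0.0076. Power is Φ(3.861 − 2.669) = Φ(1.192) = 88.3%.

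Regions are ordered North America / Asia Pacific / Europe. Shares are 60/10/30% in the first three rows and 45/10/45% in the last two.

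| Walk shift (m) | Event multipliers | η² | Actual size | Pooled power when stratified = 90% |
|---|---|---|---|---|
| none | none | 0 | 0.0099 | 90.0% |
| 0/−10/+10 | 1.1/0.8/0.9 | 0.003 | 0.0098 | 89.9% |
| 0/−20/+20 | 1.3/0.7/0.5 | 0.026 | 0.0090 | 89.4% |
| 0/−40/+40 | 1.5/0.5/0.5 | 0.066 | 0.0076 | 88.3% |
| 0/−60/+60 | 1.8/0.5/0.4 | 0.131 | 0.0057 | 86.3% |

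Simulation of the fourth row agrees: null SD of the pooled z 0.967 (predicted 0.9665), size 0.0075 pooled vs 0.0098 stratified, and power at the full design effect 94.3% vs 95.5%.

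**Step 3, simulation under a different regional mix.** Shares 45/40/15%, 6000 replicates, missing walks set to 0 m, assumed baseline distance 280 m (SD 100). Entries are pooled / van Elteren. *Moderate* is multipliers 1.25/0.8/0.9 with shifts −12/+12/+5 m. *Strong* is 1.5/0.6/0.8 with −25/+25/+10 m. *Extreme* is 2/1/0.5 with ±45 m.

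| Scenario | Null SD of z | Null rejection, % | Power, full effect, % | Power, effect × 0.91, % |
|---|---|---|---|---|
| None | 1.004 / 1.004 | 1.05 / 1.08 | 94.8 / 94.9 | 90.4 / 90.4 |
| Moderate | 0.996 / 1.004 | 0.97 / 1.02 | 95.7 / 95.9 | 89.2 / 89.6 |
| Strong | 0.956 / 0.988 | 0.62 / 0.75 | 94.6 / 95.7 | 88.6 / 90.4 |
| Extreme | 0.922 / 0.979 | 0.60 / 0.87 | 95.1 / 97.4 | 86.3–89.9 / 91.4–93.6 |

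The factor 0.91 brings power to about 90% when regions do not differ. The full-effect gains, with SE, are 0.08 (0.06), 0.23 (0.08), 1.15 (0.14) and 2.28 (0.20) points. At half the design effect, the strong case gives 28.6% vs 32.3%.

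The squared ratio of mean z gives the equivalent gain in participants: moderate (4.278/4.239)² = 1.02, strong (4.304/4.139)² = 1.08, extreme (4.470/4.099)² = 1.19. Across the extreme layouts the gain is 14 to 19%.

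**Step 4, closer to the planned missing-data rule.** Half the missing walks were set to 0 m and half multiply imputed (20 imputations, Rubin's rule, 1500 replicates, full effect). Pooled / stratified power is 97.2/97.3, 97.7/97.8, 97.5/98.1 and 97.5/98.7%. The gain is 0.1 to 0.6 points up to the strong case and 1.2 in the extreme one.

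**The case against.** The pooled test is valid, since a test at or below its nominal level makes no conclusion unsafe. It also matches the stated null, which compares a random treated participant with a random control and places no restriction on region. Nothing in the documents shows that regions differ. Because the endpoint uses change in walk distance, regional differences in walking level largely cancel. The strong case needs mean change to differ by 50 m between regions, against a design effect of 18 m, plus a 2.5-fold spread in event rates. In Step 3 the stratified test also under-rejects somewhat in the strong and extreme cases. The Monte Carlo SE is √(0.0099 × 0.9901/6000), or about 0.13 points, so not all of the shortfall in size can be put down to pooling. A few exploratory analyses (negative binomial, modified Poisson, responder chi-square) name no region adjustment either. Finally, rewriting the null of the gatekeeping endpoint is more than a programming change, and it is not evident that a numbered memo would cover it.

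Much of this stands. The gain depends on assumptions and is small in the plausible range. With a larger treatment effect in the higher-risk region, one check of the moderate scenario (1500 runs) gave 95.3% pooled vs 95.2% stratified, so no gain. What the objection does not supply is a reason to leave out of the primary test the factor that the trial randomizes by and that its other main models use.

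**Conclusion.** The point holds as a low-cost improvement in efficiency and consistency, not as a threat to validity. If regions are alike, the two tests coincide. If they differ, the pooled test is mildly conservative. With the effect scaled to 90% power, stratifying recovers about 0.4 points (moderate differences), 1.8 (strong) and 3 to 5 (extreme). At the full design effect the figures are roughly 0.2, 1.2 and 2.

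The direction follows from the design. The size rests on assumed regional shares and differences and on a constant treatment effect, and the comparison in Steps 3 and 4 left out the 2.5% annual loss to follow-up. The power argument concerns the Wilcoxon test. The win ratio only aids interpretation, and its confidence-interval formula, which the SAP takes from a cited source, was not checked.

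**What to change.** In SAP 5.3.1, before unblinding:
- Specify a region-stratified Wilcoxon (van Elteren) test in each imputed dataset, combined by Rubin's rule as already planned.
- Report a region-stratified win probability and win ratio.
- Restate the null and estimand as comparisons of participants within the same region.
- Keep the pooled test and pooled win ratio as a named sensitivity analysis, so that the all-pairs estimand is still reported.
- Align the wording of protocol 8.6.

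The cost is revised text and a stratum term in the program, with no new data or visits. Protocol 9.8.5 lets changes in statistical methods be recorded by numbered memo. Because the null also changes, the sponsor should confirm that this route is enough; protocol 10.1 gives approval of the SAP and of amendments to the Steering Committee. The trade-off is the small shift from all-pairs to within-region comparisons. The stated power need not be rerun: with a common effect across regions, the stratified test was at least as powerful in every scenario, within simulation error.
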